#### 10.5 Measures for Serious Adverse Events and Malfunctions

If an investigator or research collaborator becomes aware of the occurrence of a serious adverse event (excluding diseases or the like) or malfunction, they will take necessary measures, such as explaining the event or malfunction to the subject, and reporting the information promptly to the principal investigator. If the principal investigator becomes aware of the occurrence of a serious adverse event or malfunction, he/she will promptly report it to the head of the research site using Reference Form 1, "Report on Serious Adverse Events and Malfunctions," and take appropriate action. In addition, the principal investigator will promptly share information regarding the occurrence of the serious adverse event or malfunction with investigators and other personnel involved in the conduct of the clinical research.

#### 10.6 Measures for Diseases or the Like

If an investigator becomes aware that a subject has developed a disease or the like, they will promptly report this information to the head of the research site and the principal investigator.

When the head of the research site or the principal investigator receives a report, they will notify applicable investigators to discontinue the clinical research or take other necessary measures. In addition, the cell culturing and processing facility must be promptly notified of the situation that occurred and the measures taken.

1) Reporting to the Certified Committee for Regenerative Medicine

When the head of the research site becomes aware of any of the matters listed below, he/she will report the matter to the Certified Committee for Regenerative Medicine using Appendix Form 1 "Disease Report (for Committee Report)" within the applicable period specified in (1) to (3) below.

- (1) Occurrence of disease or the like meeting any of the following criteria that is either suspected to be caused by provision of the regenerative medicine product or result from an infectious disease suspected to be caused by the provision of the regenerative medicine product: 7 days
  - i. Results in death
  - ii. Is life-threatening
- (2) Occurrence of disease or the like meeting any of the following criteria that is either suspected to be caused by provision of the regenerative medicine product or result from an infectious disease suspected to be caused by the provision of the regenerative medicine product: 15 days
  - i. Requires hospitalization or results in prolongation of existing hospitalization
  - ii. Results in disability/incapacity
  - iii. Poses a risk of disability/incapacity
  - iv. Is serious
  - v. Is a congenital disease or anomaly in offspring
- (3) Occurrence of diseases or the like suspected to be caused by provision of the regenerative medicine product or by an infectious disease suspected to be caused by provision of the regenerative medicine product (excluding (1) and (2)): Within 10 days of the end of the applicable period every 60 days from the date of submission of the Regenerative Medicine Provision Plan to the Minister of Health, Labour and Welfare

When the head of the research site receives an opinion from the Certified Committee for Regenerative Medicine, the head of the site will report changes made to the Regenerative Medicine Provision Plan and other measures taken based on that opinion back to the Certified Committee for Regenerative Medicine.

2) Reporting to the Minister of Health, Labour and Welfare

When the head of the research site becomes aware of (1) or (2) listed in 1) above, the head of the site will report the matter to the Minister of Health, Labour and Welfare using Appendix Form 2 "Disease Report (for MHLW Report)" within the applicable period specified in (1) or (2) in 1).

# 10.7 Expected Adverse Events

# 10.7.1 Adverse events caused by transplantation surgery/procedures

1) Conjunctival hyperemia

Treatment: Topical or systemic anti-inflammatory agents

2) Subjective symptoms (eye pain, foreign body sensation, lacrimation, photophobia, dryness, and discomfort)

Treatment: Eye drops, eye ointment, or oral medication for serious cases

3) Superficial punctate keratopathy

Treatment: Eye drops or eye ointment administered locally for serious cases

4) Corneal epithelial defect

Treatment: Eye drops or eye ointment for serious cases

5) Symblepharon

Treatment: Surgical release of adhesions for serious cases

6) Conjunctivalization

Treatment: Eye drops or eye ointment as needed for serious cases

7) Infectious keratitis

Treatment: Antibiotics, antivirals, or antifungals, and surgical treatment as needed

8) Increased intraocular pressure

Treatment: Local or systemic antiglaucoma agents, and surgical treatment as needed

9) Cataract

Treatment: Surgical treatment for serious cases

10) Corneal keratinization

Treatment: Removal of corneal keratinization for serious cases

11) Endophthalmitis

Treatment: Antibiotics, antivirals, or antifungals, and surgical treatment as needed

#### 10.7.2 Adverse events caused by the specific processed cell product (iCEPS)

- 1) Allergic reaction due to use of materials of animal origin (bovine, porcine, or rodent)
  Treatment: Systemic allergic reactions should be treated by systemic antiallergic agents
  and corticosteroids, and shock should be treated by vasopressors and bronchodilators.
- 2) Infectious disease due to use of materials of human and animal origin (bovine, porcine, or rodent)

Treatment: If infectious keratitis is suspected, identification of the causative microorganism by culture of a scraped sample of the lesion and treatment by means such as topical/systemic antibiotics or graft removal may be necessary.

3) Immunological rejection

Treatment: Immunosuppressive agents and corticosteroids may be required.

- 4) Development of a neoplastic lesion
  - (1) Local (at site of iCEPS transplantation)

Treatment: Although this is considered extremely unlikely, if it does occur, appropriate treatment should be given based on the type of lesion.

# (2) Systemic

Treatment: Development outside the local area is unlikely, but if it does occur, appropriate treatment should be given based on the type of lesion.

#### 10.7.3 Adverse events caused by general anesthesia

Adverse events caused by procedures such as tracheal intubation and anesthetic use may include the following:

Dental injury, pharyngeal injury, hoarseness, bronchospasm (asthma attack), urticaria/shock symptoms, malignant hyperthermia, aspiration pneumonia, etc.

#### 11. Discontinuation of the Entire Clinical Research

#### 11.1 Discontinuation Criteria

The principal investigator will discontinue the entire clinical research in the following cases:

- 1) The principal investigator determines that there is a safety issue with the protocol treatment
- 2) Development of the specific processed cell product (iCEPS) is discontinued
- 3) The research is discontinued based on guidance or orders from regulatory authorities, the opinion of the Certified Committee for Regenerative Medicine, or the judgment of the head of the research site

#### 11.2 Discontinuation Procedures

If the decision is made to discontinue the entire clinical research, the principal investigator or subinvestigator will promptly notify the subjects and provide appropriate treatment. In addition, they will carry out necessary procedures in accordance with "16.5 Report of Discontinuation."

# 12. Case Report Forms

# 12.1 Preparation, Modification, and Correction of Case Report Forms

- 1) The principal investigator or a subinvestigator will prepare CRFs for enrolled subjects.
- 2) If the clinical research coordinator is assisting in preparing CRFs, they should only transcribe from source documents, within the scope not requiring medical judgment, and should be supervised by the principal investigator or subinvestigator.
- 3) Details are described separately in "Guidance on Preparation, Modification, and Correction of Case Report Forms."

# 12.2 Review of Case Report Forms

- 1) When a CRF is prepared by a subinvestigator, the principal investigator will inspect the contents of the form to confirm that there are no problems before submission to the Data Center and will then sign or stamp the form and submit it to the Data Center.
- 2) The principal investigator will ensure that CRFs submitted to the Data Center are accurate, complete, legible, and submitted in a timely manner, and that subject identification codes and registration numbers are used to identify subjects.

# 12.3 Submission Deadlines for Case Report Forms

The principal investigator, subinvestigators, and research collaborators will prepare a CRF promptly after the completion of each visit or at research discontinuation for the subject in question. The principal investigator will then sign or stamp the form, submit it to the Data Center, and retain a copy.

# 12.4 Specification of Case Report Form Entries That Are Regarded as Source Documents

Information on the following 1) to 7) entered directly into CRFs can be used as source documents.

- 1) Severity of comorbidities
- 2) Details of concomitant drugs and therapies
- 3) Adverse event status and details
- 4) Need for histopathological testing
- 5) Need for X-ray CT scan
- 6) Reason for discontinuation
- 7) Other comments of the investigator and subinvestigator

#### 13. Statistical Considerations

#### 13.1 Definitions of Analysis Sets

1) Safety analysis set

Includes all enrolled subjects except those meeting the criteria below:

- (1) Did not undergo iCEPS transplantation
- (2) Did not undergo any safety observations
- 2) Efficacy analysis set

Includes all enrolled subjects except those meeting the criteria below:

- (1) Did not undergo iCEPS transplantation
- (2) Did not undergo any efficacy observations after iCEPS transplantation

#### (3) Major protocol violation

#### 13.2 Analyses and Methods

All statistical analyses will be performed after data lock for all subjects.

#### 13.2.1 Disposition of subjects

The number of enrolled subjects, number of ineligible subjects, number of post-enrollment deviations, number included in analysis sets, and number of subjects who discontinued will be tabulated. Reasons will be given for subjects who had post-enrollment deviations or discontinued.

#### 13.2.2 Subject characteristics

Subject characteristics will be presented in a listing table.

#### 13.2.3 Primary endpoint (safety)

Adverse events for which data were collected will be listed for each subject (event name, onset date, outcome date, duration, outcome, severity, seriousness, causal relationship with the protocol treatment, and rationale for causality determination). The number of subjects who experienced the event and the number of events will also be shown for each adverse event. Duration is defined as "outcome date – onset date + 1 (day)." Serious adverse events will be tabulated in a similar fashion.

Neoplastic lesion status and rejection status at each time point will also be listed, along with details of relevant laboratory results.

#### 13.2.4 Secondary endpoints (efficacy)

A time course of severity will be shown in a table and line graph for the following items defined in "9.2 Secondary Endpoints": 1) LSCD stage, 2) severity of corneal epithelial defect, 3) subjective symptoms, 6) degree of corneal opacification, 7) degree of corneal neovascularization, and 8) degree of symblepharon. For "4) Corrected distance visual acuity," measured values and the magnitude of change from baseline over time will be shown in a table and line graph. For "5) QOL," the 12-item subscale scores on the NEI VFQ-25 will be calculated, and the overall score will be calculated from 10 subscales excluding "general health" and "driving." In addition, summary statistics for overall score at baseline and at Week 52 after iCEPS transplantation or the discontinuation date will be calculated and evaluated. Baseline is defined as the day of transplantation (before transplantation).

# 13.3 Significance Level To Be Used

No estimations or tests that would require setting of confidence coefficients or significance levels will be used in this research. Instead, descriptive methods will be used in analysis.

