# 1. Objectives

To confirm the safety of transplantation of the specific processed cell product (induced pluripotent stem cell-derived corneal epithelial cell sheet [iCEPS]) in patients diagnosed with limbal stem cell deficiency (LSCD), evaluate the efficacy, and explore the feasibility of the protocol treatment.

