#### 2.2.1 Allogeneic limbal transplantation

In this therapy, the conjunctival pannus is completely removed from the injured eye, and limbal tissue collected from a cornea donor is transplanted. The limbus covers the cornea of the injured eye and protects the cornea from invasion of conjunctival tissue or invasive cells. However, this therapy has two major problems. The first problem is rejection. It is known that limbal transplantation shows a high rejection rate (17-52%) when used in patients with LSCD, a disease of the corneal epithelium. Even if an immunosuppressive agent is administered, a long-term therapeutic effect cannot be expected, and prognosis is poor. Another problem is shortage of donors. The Japan Eye Bank Association reported that 1,624 patients are waiting for transplantation as of the end of 2017, but only 869 persons donate their eyes a year, indicating a serious shortage of donors.

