homogenized iPS cells and dramatically reduces the time required to generate therapeutic cells.

However, the only iPS cell lines currently available for clinical use are established from HLA-homozygous donors covering the most common haplotypes in the Japanese population, which limits the number of patients who can receive HLA-matched transplantations. As the specific processed cell product to be transplanted in this clinical research consists solely of epithelial cells, rejection should be less likely in allogeneic transplantation than in donor limbal transplantation, which involves transplantation of the corneal epithelium, corneal parenchyma, and limbus. In addition, use of immunosuppressive agents may further reduce the incidence of rejection. Based on the above rationale, this clinical research will evaluate the safety and efficacy of iCEPS transplantation in combination with immunosuppressive agents in patients whose HLA type is mismatched with iPS cells derived from homozygous donors (cases 1 and 2). For cases 3 and 4, the patient's HLA type and use of immunosuppressive agents will be determined based on the results of midterm evaluation of cases 1 and 2 in order to ensure the subjects' safety. Once the safety of iCEPS transplantation is confirmed through this clinical research and the effects of HLA compatibility and need for use of immunosuppressive agents are clarified, we plan to optimize the treatment design based on those findings and evaluate the therapeutic effects of iCEPS transplantation in the next phases of clinical trials.

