# 7. Planned Sample Size and Research Period

Planned sample size: 4 subjects

Research period: May 23, 2019 to March 31, 2024

Follow-up period: 1 year (52 weeks) after iCEPS transplantation

Additional safety monitoring period: 1 year (52 weeks) after the end of the follow-up period

\*After follow-up is complete, subjects will be encouraged to make regular outpatient visits and participate in follow-up throughout their lives as much as possible so that data can be collected and appropriate measures are taken as needed. Data collected through follow-up surveys will not be included in the analysis of results for this clinical research.

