#### [Rationale for setting]

Osaka University Hospital, the site for this research, sees approximately 100 patients with LSCD each year.

Of these, only about 10% (10 patients) would likely be eligible for the protocol treatment. If we estimate that 20% of these eligible candidates would enroll, we would expect to be able to recruit 2 subjects per year. Therefore, the target sample size was set as 4 subjects.

The additional safety monitoring period of one year (52 weeks) was set in consideration of the following.

1) Overseas research of autologous cultivated corneal epithelial cell sheet transplantation

showed that if the reconstructed corneal epithelium is stable for one year after transplantation, stability of the corneal epithelium can be maintained thereafter, confirming a sustained therapeutic effect).

- 2) A report of long-term outcomes of autologous cultivated oral mucosal epithelial cell sheet transplantation showed that conjunctivalization, corneal opacity, and corneal neovascularization rates stabilize from one year after transplantation, with few changes.
- 3) As an follow-up period of about 6 months is generally required after ophthalmic surgery, 52 weeks can be considered a sufficient period to confirm safety.
- 4) A nonclinical tumorigenicity study of iCEPS, the specific processed cell product used in this research, showed no tumorigenesis in mice for 4 months after transplantation (see "5.3 Overview of Preclinical Study Results"). For the first-in-human transplantation of iCEPS, we believe that a safety confirmation period of 1 year (52 weeks) is reasonable, considering 1) to 3) above. A additional safety monitoring period of one year will be set, but follow-up will continue as long as possible thereafter to confirm the long-term safety of iCEPS.

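### The plan says safety will be confirmed, but event counts in four patients without confidence limits cannot support that conclusion

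*Combined protocol and SAP*

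**What the plan says.** The first aim in section 1, repeated in the Synopsis, is "To confirm the safety of transplantation of the specific processed cell product". Section 2.4 looks ahead from that result: "Once the safety of iCEPS transplantation is confirmed through this clinical research", and once the roles of HLA compatibility and immunosuppression are clear, the treatment design is to be optimised and later trial phases run.

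The primary endpoint (9.1) is adverse-event data to week 52. Section 13.2.3 lists each event by subject, gives the number of subjects and events, does the same for serious adverse events, and lists rejection and neoplastic lesion status at each time point. Section 13.3 then says: "No estimations or tests that would require setting of confidence coefficients or significance levels will be used in this research".

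Section 7 gives "Planned sample size: 4 subjects". Its rationale is recruitment: the site "sees approximately 100 patients with LSCD each year", and "Of these, only about 10% (10 patients) would likely be eligible for the protocol treatment", of whom a fifth are expected to enrol. I found no acceptable event rate, no margin, and no statement of which rates four patients could exclude.

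Section 2.2.1 supplies the one rejection figure that serves as a yardstick: "limbal transplantation shows a high rejection rate (17-52%) when used in patients with LSCD". Under sections 3.2.1 and 6.2, cases 1 and 2 receive cyclosporine. If neither has uncontrolled rejection, cases 3 and 4 do not.

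**The concern.** Confirming safety implies that unacceptable event rates have been ruled out. The plan names no such rate, chooses the sample size without regard to precision, and excludes the one summary that would show how little a count out of four can rule out. The conclusion in sections 1 and 2.4 is therefore not tied to anything the analysis in section 13 produces.

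The practical stake is the decision in section 2.4 to move on to later phases. If few or no events are seen, the report would carry the word *confirmed* without any figure for the rates that remain compatible with the data. The difficulty is greatest for rejection, because the study changes the immunosuppression regimen halfway when the first two cases go well.

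**Working it through.** **Inputs.** n = 4 (section 7). Recruitment figures of 100 patients per year, 10% eligible and 20% enrolling (section 7, rationale). Yardstick range 17% to 52% (section 2.2.1). Regimen rule (3.2.1, 6.2). No confidence level is set in the plan; I use 95% and show alternatives.

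**The plan's own figure.** 100 × 0.10 × 0.20 = 2 subjects per year; two years give 4. This reproduces the sample size. The two-year window is implied, not stated. No error rate, power or margin enters.

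**Upper limit with no events.** The exact (Clopper-Pearson) limit U solves (1 − U)^n = α, so U = 1 − α^(1/n).

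| Result | One-sided 90% | One-sided 95% | Two-sided 95% |
|---|---|---|---|
| 0/4 | 43.8% | 52.7% | 60.2% |
| 0/2 | 68.4% | 77.6% | 84.2% |

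For example, 1 − 0.05^(1/4) = 0.527 and 1 − 0.05^(1/2) = 0.776. One event in four has a one-sided 95% limit of 75.1% (the 0.95 quantile of Beta(2, 3)).

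**Chance of seeing no events,** (1 − p)^n:

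| True rate p | 0/4 | 0/2 |
|---|---|---|
| 5% | 81.5% | 90.3% |
| 10% | 65.6% | 81.0% |
| 17% | 47.5% | 68.9% |
| 52% | 5.3% | 23.0% |

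The true rate at which four patients show at least one event with 80% probability is 1 − 0.20^(1/4) = 33%.

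**Patients needed.** To exclude 17% with no events at one-sided 95%: ln 0.05 / ln 0.83 = 16.1, so 17 patients.

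**Why rejection should not simply be pooled.** No rejection in four patients implies no uncontrolled rejection in cases 1 and 2, and that is the branch in which cases 3 and 4 receive no cyclosporine. A clean 0/4 for rejection is therefore always, as planned, 0/2 with cyclosporine and 0/2 without. The limit for each regimen is 77.6%, and the pooled 52.7% describes a mixture of the two.

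**The case against.** The case for leaving the plan alone has real substance.

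- **Descriptive analysis suits the study.** Listing every event by subject, without tests, is a coherent choice for an uncontrolled first-in-human study of four. This stands. Neither n = 4 nor the absence of tests is the fault. It is also true that the limit for zero events is fixed by n and can be worked out by any reader, but that is no reason to exclude it from the report.
- **The plan nowhere says that zero events means safe.** A reader might infer that a clean result would be taken as proof and would by itself trigger the next phase. The documents do not support that. There is no pass criterion. Section 9.1 and the supplement's study design speak of evaluating safety, and the final evaluation (9.5) includes a physician not directly involved in the research. Section 7 adds a second monitoring year and continued follow-up.
- **The word may be loose.** The protocol elsewhere uses *confirm* to mean *check*, as for sheet attachment (6.1) and medication compliance (6.2). That reading is possible in section 1, but fits section 2.4 poorly, where confirmation is a condition for what follows.
- **The 17% to 52% range belongs to a different graft.** Section 2.4 expects less rejection with an epithelium-only product, and section 2.2.1 gives neither the definition of rejection nor the follow-up. It is a yardstick, not a comparator. A reader might also infer that 0/4 cannot exclude even 52%. That rests on 52.7% against 52% at one level; at one-sided 90% the limit is 43.8%. The low end is the sound comparison, since 17% is not excluded at any of these levels.
- **The remark in section 7 that 52 weeks suffices** justifies the length of follow-up. It says nothing about the number of patients and is not evidence for this point.

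**Conclusion.** The point holds as a mismatch between the stated conclusion and what the design can deliver. Four patients with no events leave rates up to 52.7% unexcluded (one-sided 95%; 60.2% for a two-sided interval), and a true rate of 17% would give that result in 47% of trials. For rejection, each regimen has two patients and a limit of 77.6% when no rejection is seen.

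These figures assume independent patients with a common event rate within each group counted. They concern risk over the 52-week evaluation period. They do not show that the treatment is unsafe, that the sample size is wrong for a first study, or that the sponsor would treat a clean result as proof. The change should be made because the wording reaches further than the data can, and correcting it is cheap.

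**What to change.** 1. **Synopsis, sections 1 and 2.4.** Replace the wording about confirming safety, or safety being confirmed, with *evaluate safety* or *obtain initial safety data*.
2. **Section 13.3.** Keep the exclusion of hypothesis tests but allow exact limits, for example: *No hypothesis tests will be done. For rejection, neoplastic lesion and serious adverse events, the number of subjects with the event will be shown with an exact (Clopper-Pearson) one-sided 95% upper limit.*
3. **Section 13.2.3.** Show these limits beside the subject counts. Give rejection by immunosuppression regimen, and label any pooled figure as mixing regimens. State which event rates the data cannot exclude; with 0/4 these are all rates up to about 53%, and with 0/2 up to about 78%.

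Section 13.5 gives the route: a protocol revision, with the reason explained in the clinical study report. The limits need only the counts already planned, so they can also be calculated from collected data for that report.

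The cost is a few lines of text and a few exact limits, with no extra patients, visits or procedures. The downside is a less favourable safety statement and limits so wide that they mainly show how much remains unknown.
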